12.6.1. Immunogenicity

A by-visit summary will present descriptive statistics for the actual and change from Baseline results by visit and treatment group for IgG, IgA, IgM, HAHA, high sensitivity C-reactive protein (hsCRP), and B-lymphocyte chemokine (BLC). Additionally, descriptive statistics will be used to summarize each subject's largest decrease from Baseline. The number and percentage of subjects below the LLN at each visit, below the LLN at any time during the on-therapy period and below the LLN during the first 12 weeks of treatment will be presented by treatment group.

All immunogenicity data will be presented in a data listing.

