6.3. Safety

The following safety endpoints will be assessed:

[figure not shown]
- Adverse events
- Adverse event frequency, severity, and relationship to investigational product
- Frequency and severity of infections
- Frequency of SAEs
- Frequency of withdrawals due to treatment-related AEs.
- Frequency of AEs leading to permanent discontinuation of investigational product.
- Frequency of AEs of special interest, postinjection systemic reactions, and injection site reactions.
- Change from baseline in vital signs.

- Frequency of vital signs of clinical concern.
- Change from baseline in laboratory (hematology, chemistry, and urinalysis) parameters.
- Frequency of laboratory (hematology, chemistry, and urinalysis) results of potential clinical concern.
- Immunogenicity as measured by the incidence, titer, and type of HAHA immune response.

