2.1.4. Secondary Objectives - Safety

- To evaluate the immunogenicity of ofatumumab SC.
- To evaluate the safety and tolerability of ofatumumab SC.

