2.2.1. Co-Primary Efficacy Endpoints

Some of the analysis bullet points described in the original protocol is removed as requested by Novartis (section 2.2.2 - 2.2.6).

Two co-primary efficacy endpoints will be evaluated:

- Time to SR on minimal steroid therapy (defined as time from randomization to the time the subject initially tapered his/her oral prednisone/prednisolone dose to ≤ 10 mg/day and maintained ≤ 10 mg/day of oral prednisone/prednisolone with no new or nonhealing (established) lesions for ≥ 8 weeks AND maintained that status until Week 60).
- Duration of remission on minimal steroid therapy (defined as total time [sum] of all periods of remission while on minimal steroid therapy [oral prednisone/prednisolone dose of ≤ 10 mg/day] up to Week 60).

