2.2.4. Safety Endpoints

- All AEs
- Frequency of serious adverse events (SAEs).
- Change from Baseline in vital signs.
- Change from Baseline in laboratory (hematology, chemistry, and urinalysis) parameters.
- Immunogenicity as measured by the incidence, titer, and type of human anti-human antibody (HAHA) immune response.

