9.2. Derived and Transformed Data

9.2.1. Change from Baseline

The baseline value for an assessment is defined as the last non-missing value before the start of treatment. Change from Baseline is defined as the post-baseline value minus the baseline value for the given assessment. If either the baseline or post-baseline value is missing then the change from baseline value will also be missing.

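### SAP 12.6.1 gives HAHA an actual-value and change-from-baseline summary, which does not match the retained endpoint of incidence, titer and type in SAP 2.2.4

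*SAP*

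**What the plan says.** **Objective and endpoint.** SAP 2.1.4 lists as a secondary safety objective: "To evaluate the immunogenicity of ofatumumab SC". SAP 2.2.4 gives the endpoint as "Immunogenicity as measured by the incidence, titer, and type of human anti-human antibody (HAHA) immune response". Protocol 6.3 uses the same three components: "Immunogenicity as measured by the incidence, titer, and type of HAHA immune response".

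**Analysis.** SAP 12.6.1 is the only part of the SAP that assigns HAHA an analysis. It plans descriptive statistics for actual and change-from-baseline results "by visit and treatment group for IgG, IgA, IgM, HAHA, high sensitivity C-reactive protein (hsCRP), and B-lymphocyte chemokine (BLC"). It then adds each subject's largest fall from baseline and "The number and percentage of subjects below the LLN at each visit", with further below-LLN counts over the on-therapy period and the first 12 weeks. It ends with a listing of all immunogenicity data. Neither the largest-fall sentence nor the LLN sentence names an analyte.

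**What change means.** SAP 9.2.1 states: "Change from Baseline is defined as the post-baseline value minus the baseline value for the given assessment".

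**Pruning after early termination.** SAP 1 says the plan was reduced or simplified because the study stopped with 69 patients. SAP 2.2.1 adds: "Some of the analysis bullet points described in the original protocol is removed as requested by Novartis", with reference to sections 2.2.2 to 2.2.6. The HAHA bullet in 2.2.4 survived that cut.

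**The concern.** The endpoint asks three things about an antibody response: how many subjects have one, how strong it is, and of what type. The analysis section answers a different question, namely how far a measured level moves from its baseline value. That suits IgG, IgA and IgM, which share the paragraph and for which a falling level is what matters. For anti-drug antibody the interest is in a new or rising response.

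HAHA is named in the text and given a method, so a programmer following the SAP would build a by-visit change table and would have no instruction to count antibody-positive subjects. A secondary safety objective for a monoclonal antibody could then reach the report with no incidence by treatment group, leaving the reader to derive it from a listing.

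**Working it through.** No figure is at issue, so the check sets the endpoint against every analysis statement that could deliver it.

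**1. Specific text, by component**

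| Endpoint component (SAP 2.2.4) | Summary specified in SAP 12.6.1 | Other route |
|---|---|---|
| Incidence | None; HAHA-positive is not defined | By-subject listing |
| Titer | Not explicit; present only if the actual result is a titer | By-subject listing |
| Type | None | By-subject listing |

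Two of the three components have no specified summary, and the third depends on something the SAP does not state.

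**2. What the stated method would yield.** Neither document describes the form of the HAHA result, so both plausible forms are taken in turn.

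- *Result is positive/negative.* The subtraction in SAP 9.2.1 has no meaning. The actual-value half could become a by-visit count if descriptive statistics are taken to include counts. It would still not give the number of subjects positive at any post-baseline time, nor the type.
- *Result is a titer.* Titer would be described by visit, but incidence and type would not. The SAP also does not say what value a negative sample takes in the subtraction.

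Neither form delivers all three components.

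**3. General statements.** Protocol 8.3.6.9 lists the planned safety summaries and contains none for HAHA. Protocol 8.3.6.10 promises summary statistics for remaining endpoints without a method. SAP 12.6 restricts its descriptive statistics to hematology, chemistry and urinalysis tests with a quantitative result, and its closing sentence on laboratory assessments gives no HAHA method.

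**4. Scope of the LLN and largest-fall sentences.** Protocol Appendix 13 gives lower limits for IgG (694 mg/dL), IgM (48 mg/dL) and IgA (81 mg/dL). hsCRP has only an upper bound (below 3.1 mg/L), BLC is marked as having no established range, and HAHA has no entry. So 3 of the 6 analytes in the paragraph have an LLN, and the LLN count can work only for the immunoglobulins.

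**5. Was the endpoint dropped on purpose?** Where the sponsor dropped analyses, it said so. The SAP modification history names two pharmacodynamic endpoints whose analyses will not be done and records the removal of the pharmacogenetic section. It contains no such statement for HAHA.

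**The case against.** The best defence is that 12.6.1 is loosely drafted rather than wrong. Descriptive statistics are nowhere confined to means. Protocol 8.3.6.5, although written for efficacy, summarizes categorical data by counts and percentages, and a by-visit positive/negative count could fall within the actual results. A titer could appear there too. Table shells existed when the SAP was finalized (SAP 1) and may already define a HAHA display. The raw data are listed, safety data receive no inferential analysis, and the trial ended with 69 randomized subjects.

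Much of this stands, and it rules out two stronger conclusions that a reader might draw.

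- *That no component of the endpoint would be reported.* The documents do not support this. All data are listed, and a count or a titer may surface among the actual results.
- *That HAHA will be counted against a lower limit of normal.* The LLN sentence names no analyte and, given Appendix 13, can sensibly cover only IgG, IgA and IgM. The same reading fits the largest-fall sentence.

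What does not stand is the suggestion that only detail is missing. HAHA is explicitly placed in a change-from-baseline summary, and no sentence in either document assigns it a count of positives or a tabulation by type. Early termination is a good reason to simplify, but the endpoint was kept, and a count table is simpler than the table now planned.

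**Conclusion.** Wrong as written, with minor impact. The analysis in SAP 12.6.1 does not deliver the secondary safety endpoint in SAP 2.2.4: no summary of HAHA incidence or type by arm is specified, titer is not explicitly summarized, and otherwise only a by-subject listing is planned. The co-primary conclusions do not depend on it.

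This rests on the SAP and protocol text alone. The table shells are not available and could already contain a suitable display, in which case the SAP text would need to be brought into line with them. The form in which HAHA results are reported is also not stated. As the working shows, the mismatch remains whether the result is positive/negative or a titer.

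**What to change.** In SAP 12.6.1:

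1. Remove HAHA from the change-from-baseline summary.
2. State that the largest-decrease and below-LLN summaries apply only to IgG, IgA and IgM.
3. Define a HAHA-positive result, and tabulate by treatment group n/N (%) positive at baseline, at any post-baseline time, and by visit. Give titer and type among positives, as reported by the assay.

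A category for persistent positivity goes beyond the stated endpoint and is optional.

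If the sponsor prefers not to add a table, amend SAP 2.2.4 to say that the endpoint is reduced to a listing because of early termination.

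The cost is one replacement table and a few sentences. Protocol Table 6-1 already schedules HAHA sampling at baseline and repeatedly afterwards, so no new collection is needed, provided that titer and type results are delivered in a form that can be tabulated; the documents do not confirm this.

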7. Past or current malignancy, except for:
- Cervical carcinoma Stage 1B or less.
 - Noninvasive basal cell and squamous cell skin carcinoma.
 - Cancer diagnoses with a duration of complete response (remission) >5 years.
Note: A history of hematologic malignancy excludes a subject from participation, regardless of response.
8. Significant concurrent, uncontrolled medical condition that could affect the subject’s safety, impair the subject’s reliable participation in the study, impair the evaluation of endpoints, or necessitate the use of medication not allowed by the protocol.

9. Any of the following screening laboratory values:
 - White blood cells <3.8 GI/L ($<3800/\text{mm}^3$).
 - Neutrophils <2 GI/L ($<2000/\text{mm}^3$).
 - Platelets <130 GI/L ($<130,000/\text{mm}^3$).
 - Circulating IgG, IgA, or IgM levels $<10\%$ of the LLN and requiring treatment in the opinion of the investigator.
 - Alanine aminotransferase (ALT) >2.0 times the upper limit of normal (ULN).
 - Aspartate aminotransferase $>2.0 \times$ ULN.
 - Alkaline phosphatase $>1.5 \times$ ULN.
 - Bilirubin $>1.5 \times$ ULN (except in cases of isolated predominantly indirect hyperbilirubinemia due to Gilbert's syndrome).
10. Use of an investigational drug or other experimental therapy within 4 weeks, 5 pharmacokinetic half-lives, or the duration of biological effect (whichever is longer) prior to Screening.
11. Electrocardiogram (ECG) showing a clinically significant abnormality or showing a corrected QT interval (QTc) ≥ 450 msec (≥ 480 msec for subjects with a bundle branch block) (ECG to be obtained during Screening/prior to receiving the first dose of study drug).
12. Woman who is breastfeeding.

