Abbreviations: AE=adverse event; ██████████; HBV=hepatitis B virus; Ig=immunoglobulin; PML=progressive multifocal leukoencephalopathy; PRN=as needed/as indicated; PV=pemphigus vulgaris; SAE=serious adverse event; SC=subcutaneous; WD=withdrawal.

- Subjects entering the Individualized Follow-up Period will continue to be monitored every 12 weeks, until CD19+ B-lymphocyte counts and IgG recover to \geq lower limit of normal (LLN) or to the subject's Baseline value (if <LLN) or if criteria for study withdrawal are met or for a maximum of 2 years after the last dose of ofatumumab SC.
- AEs (including AEs of special interest) and SAEs will be collected during the first year of the Individualized Follow-up Period. Only SAEs and AEs of special interest will be collected during the second year of the Individualized Follow-up Period. Any SAEs assessed as related to study participation will be collected from the time a subject consents to participate in the study up to and including any follow-up contact.

Note: Visits during Individualized Follow-up to be scheduled within ± 7 days.

Table 6-3 Time and Events Table: Pharmacokinetic-Pharmacodynamic Substudy

Period:	Baseline		Treatment Period (56 Weeks)																	F-up	Early WD
Visit Window:			±2 hours					±3 days													
Time Point:	Day 0 predose	Day 0 postdose	Day 1	Day 2	Day 3	Day 4	Day 7/ Week 1	Week 2	Week 4	Week 8	Week 12	Week 16	Week 20	Week 24	Week 36	Week 48	Week 52	Week 56	Week 60		
Pharmacokinetic sample ^a – regularly scheduled visits	X ^{a,b}							X	X	X	X	X	X	X	X	X	X	X	X	X	X
Pharmacokinetic sample – additional visits		X ^b	X	X	X	X	X														
Pharmacodynamic sample ^a – B-lymphocyte subset analyses	X								X	X	X	X	X	X	X	X	X	X	X	X	X
Adverse events	X	X	X	X	X	X	X	X	X	X	X	X	X	X	X	X	X	X	X	X	X

Abbreviations: F-up=follow-up visit; WD=withdrawal

a. Collect sample predose on dosing days.

b. Day 0 blood draws will occur predose and 4 hours postdose.

Note: from Day 1 through Day 7, pharmacokinetic samples should be collected at the same time of day (±2 hours) that the initial dose of investigational product was administered;

Week 2 through Week 60 visits should be scheduled within ±3 days of the specified time point.

****Refer to the full Time and Events table (Table 6-1) for the complete list of assessments to be performed at the regularly scheduled visits****

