8.3.6.9. Safety Analyses

The analysis of safety data will use the Safety population. These data will not undergo any formal statistical analysis.

Adverse Events

Adverse events will be coded using the MedDRA and summarized by system organ class and preferred term.

Summaries by treatment groups, of the number and percentage of subjects with the following AEs will be provided:

- All AEs
- Adverse event frequency, severity, and relationship to investigational product
- Frequency and severity of infections
- Frequency of SAEs
- Percentage of subjects withdrawing due to AEs assessed by the investigators as at least possibly related to treatment
- Adverse events leading to permanent discontinuation of investigational product
- Adverse events of special interest (see Section 6.3.2.3)
- Postinjection systemic reactions
- Injection site reactions

The hierarchical relationship between MedDRA, system organ classes, and preferred terms and verbatim text will be displayed for relevant AEs.

Clinical Laboratory Evaluations

Summary statistics will be presented for each laboratory test, and change from baseline, at each assessment time point by treatment group. Laboratory test values will be flagged to show whether they are a value within, below, or above the normal range and if they are a value of potential clinical concern. The number and percentage of subjects with values in each of these categories at each assessment time point will be summarized for each laboratory test.

Vital Signs

Each variable and change from baseline in each variable will be summarized at each assessment time point by treatment group. In addition, the number and percentage of subjects with vital sign values within, below, and above values of potential clinical concern will be summarized for each variable.

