9.3.2. Therapy Periods

For classifying AEs, infections, injection site reactions, cardiac events, liver events, medications, and non-drug therapies, the therapy periods will be defined as:

- **Pre-therapy:** If the onset date of the event is before the start date of study medication, the event will be considered pre-therapy. If the onset date of the event is on the start date of study medication, the event will be considered as on-therapy.
- **On-therapy (Treatment-emergent):** If the onset date of the event is on or after the start date of study medication and on or before 4 weeks after the date of last dose, the event will be considered on-therapy.

- **Follow-up:** For all subjects who do not enter the Individualized Follow-up Period, if the onset date of the event is after 4 weeks after the date of last dose, the event will be considered a follow-up event.
- **Individualized Follow-up:** For all subjects identified as entering the Individualized Follow-up period, events with an onset date after 4 weeks after the date of last dose will be considered individualized follow-up events.

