9.3.3. Visit Slotting Algorithm

For all safety and efficacy parameters to be summarized or analyzed by visit, data records will be slotted to one of the protocol specified visits using the following algorithm

- Determine the therapy period and study day for all records using the algorithms from Section 9.3.1 and Section 9.3.2.
- For all records (including unscheduled visit records, early withdrawal records and repeat visit records), use the therapy period and study day determined above with the slotting intervals in the analysis visit window table below to slot the record to the appropriate analysis visit.
 - For records determined to be during the pre-therapy period, the analysis visits will be based on the nominal visits recorded in the eCRF. The Baseline analysis visit will be assigned based on the study day slotting intervals as shown in the table below.
 - For records determined to be during the on-therapy period, use the study day with the slotting intervals in the table below to assign the records to the appropriate on-therapy analysis visit.
 - For records determined to be during the follow-up period, use the study day with the slotting intervals in the table below to assign the records to the appropriate follow-up period analysis visit.
 - For records determined to be during the individualized follow-up period, use the study day with the slotting intervals in the table below to assign the records to the appropriate individualized follow-up period analysis visit.

Table 9-1 Analysis Visit Windows

Scheduled Visit	Target Study Day of Visit	Slotting Intervals
Screening	-84 to -4	Not applicable
Baseline (Week 0)	1	-3 to 1 days
Week 2	15	2 to 22 days
Week 4	29	23 to 36 days
Week 6	43	37 to 50 days
Week 8	57	51 to 64 days
Week 10	71	65 to 78 days
Week 12	85	79 to 92 days
Week 14	99	93 to 106 days
Week 16	113	107 to 120 days
Week 18	127	121 to 134 days

Scheduled Visit	Target Study Day of Visit	Slotting Intervals
Week 20	141	135 to 148 days
Week 22	155	149 to 162 days
Week 24	169	163 to 176 days
Week 28	190	177 to 204 days
Week 32	218	205 to 232 days
Week 36	246	233 to 260 days
Week 40	274	261 to 288 days
Week 44	302	289 to 316 days
Week 48	330	317 to 344 days
Week 52	358	345 to 372 days
Week 56 *	386	373 to 400 days
Week 60** (End of Core Study Period) Subject has completed.	414	401 to 428 days

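### SAP 12.6.1 counts immunoglobulins below the LLN on therapy without regard to baseline, so the SAP text plans no by-arm count of subjects who became low (minor)

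*SAP*

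**What the plan says.** SAP 12.6.1 covers IgG, IgA, IgM, HAHA, hsCRP and B-lymphocyte chemokine. It plans descriptive statistics by visit for values and changes from baseline, each subject's largest fall from baseline, and a listing. It adds three counts: "The number and percentage of subjects below the LLN at each visit, below the LLN at any time during the on-therapy period", and the number "below the LLN during the first 12 weeks of treatment will be presented by treatment group". No baseline condition is attached to any of them.

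Protocol 8.3.6.9 flags each laboratory value against its normal range and adds: "The number and percentage of subjects with values in each of these categories at each assessment time point will be summarized". That is also a count per time point, not a shift from baseline. SAP 12.6 plans descriptive statistics and changes only.

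On entry, protocol 4.3 criterion 9 excludes a subject for low immunoglobulins only when a level is under 10% of "LLN and requiring treatment in the opinion of the investigator". On exit from Individualized Follow-up, the footnote to protocol Table 6-2 sets recovery at the LLN or the subject's "Baseline value (if <LLN) or if criteria for study withdrawal are met".

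SAP 9.2.1 defines baseline: "The baseline value for an assessment is defined as the last non-missing value before the start of treatment".

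**The concern.** Ofatumumab depletes B cells, so a natural safety question is how many subjects moved from a normal to a low immunoglobulin level on drug and on placebo. A count of subjects below LLN while on therapy does not answer it if some were already below LLN before the first dose. A subject who enters low and stays low is counted in the same way as one who falls below the limit during treatment.

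What is at stake is the reading of one descriptive safety table. The 12-week count has a further gap. SAP 12.6.1 does not say on which day the period ends, and the only scheduled post-baseline immunoglobulin sample in it falls at its edge.

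**Working it through.** **Which parameters have an LLN.** Protocol Appendix 13 gives lower limits of 694 mg/dL (IgG), 48 mg/dL (IgM) and 81 mg/dL (IgA). hsCRP has only an upper limit, and B-lymphocyte chemokine has no established range. The below-LLN counts therefore concern the three immunoglobulins.

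**Can a subject enter below LLN?** Ten percent of the listed limits is:
- IgG: 0.10 × 694 = 69.4 mg/dL
- IgM: 0.10 × 48 = 4.8 mg/dL
- IgA: 0.10 × 81 = 8.1 mg/dL

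Exclusion needs a level under that floor and also a need for treatment. An IgG of, say, 500 mg/dL is below LLN and eligible. Appendix 13 refers sites to the laboratory manual for current ranges, so the exact figures may differ; the conclusion does not depend on them.

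**Do the planned counts give the number newly low?** For one arm and one immunoglobulin, let n be the number of subjects, b the number low at baseline and a the number low on therapy. The number low at both lies between max(0, a + b − n) and min(a, b). Newly low is a minus that overlap, so it lies between max(0, a − b) and min(a, n − b).

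Assumed illustration: n = 35 (69 randomized, 69/2 = 34.5, equal split assumed) and a = 10.

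| b | Newly low |
|---|---|
| 0 | 10 |
| 2 | 8 to 10 |
| 4 | 6 to 10 |
| 7 | 3 to 10 |

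The number is fixed only when nobody is low at baseline, or when something further is known about the overlap. Subtracting the Baseline-visit count gives a − b, the lower end. It is exact only if every baseline-low subject is also counted as low on therapy.

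**Is that guaranteed?** SAP 9.3.2 puts the first-dose date on therapy: "If the onset date of the event is on the start date of study medication, the event will be considered as on-therapy". That rule is written for events, but SAP 9.3.3 extends the periods to visit records: "Determine the therapy period and study day for all records using the algorithms from Section 9.3.1 and Section 9.3.2". SAP 9.2.1 and Table 9-1 (Baseline window Day −3 to Day 1) treat a sample from that day as baseline if it precedes dosing. The text thus leaves open whether a first-dose-day sample counts as on therapy. This is a tension in wording, not a separate error.

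**Effect on the between-arm difference.** Let p be the share low at baseline, q the onset rate among the rest, and r the share of baseline-low subjects also counted as low on therapy. The on-therapy percentage is p·r + (1 − p)·q. With assumed p = 10% and q = 30% on drug against 10% on placebo, the difference in q is 20 points.
- r = 1 in both arms: 10 + 27 = 37% against 10 + 9 = 19%, a difference of 18 points.
- r = 1 on drug and 0.5 on placebo: 37% against 5 + 9 = 14%, a difference of 23 points.

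The planned difference can fall on either side of 20 points. Nothing in the documents fixes p, q or r.

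**The 12-week count.** In protocol Table 6-1 the immunoglobulin row is marked at Screening, Day 0 and then Week 12. SAP Table 9-1 targets Week 12 at Day 85 with a window of Days 79 to 92. Twelve weeks is 12 × 7 = 84 days. Read as Days 1 to 84, the period would exclude a Week 12 sample taken on its target day.

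**The case against.** The strongest reply is that the SAP does not call these counts treatment-emergent. The share of subjects below LLN beside a randomized placebo arm is a legitimate descriptive summary, and randomization should roughly balance those who enter low. The same section plans change from baseline, largest fall from baseline and a full listing, and Baseline is itself an analysis visit. SAP section 1 says openly that the analysis was simplified after early termination with 69 patients.

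Much of this stands, and it is why the point is minor. It does not supply the missing number. Change and largest fall are continuous summaries that do not count crossings of the LLN, and a listing is not a result by arm.

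Three further cautions are right:
- SAP section 1 refers to separate table, listing and figure documents that are not available here, so the claim is limited to the SAP text.
- The Table 6-2 exit rule covers CD19+ counts as well as IgG. It allows for a low baseline but does not show that low baseline IgG was expected.
- The instruction to collect samples before dosing (Table 6-1, footnote g) is not attached to the immunoglobulin row, so it should not be assumed that the Day 0 sample is predose.

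A reader might also infer that pre-existing lows dilute the between-arm difference. That follows only if r is the same in both arms. With unequal r the difference can instead be inflated, as the 23-point case shows.

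**Conclusion.** The point holds as a minor, inexpensive improvement. The SAP's on-therapy and 12-week below-LLN counts take no account of baseline, subjects below LLN may enroll, and the SAP text plans no by-arm count of subjects who became low. The conclusion rests on reading criterion 9 as requiring both conditions, which is how it is worded, and on the visible SAP and protocol text.

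The size is unknown and could be zero if no subject was low at baseline. The illustrations use assumed counts and rates and are not estimates for this trial. The documents do not support a claim that the treatment comparison is biased in a particular direction. Safety data receive no inferential analysis under SAP section 12, so no test or decision rule is affected. Exit from follow-up is governed by its own rule and does not use these counts.

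**What to change.** In SAP 12.6.1, for each of IgG, IgA and IgM:
- Report by arm n (%) below LLN on post-baseline samples, on therapy and in the first 12 weeks, among subjects at or above LLN at baseline.
- Add a shift table from baseline category to worst on-therapy category.
- State that baseline is the SAP 9.2.1 value, the last one before the first dose, and that this sample is not counted as on therapy.
- Define the 12-week period as running through the Week 12 analysis window (Days 79 to 92), so that the one scheduled post-baseline sample in it is always included.

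The existing counts can stay beside these. The cost is some SAP wording and one extra table. No new data are needed, and the denominator for the newly-low percentage is slightly smaller.
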